### **5.3 Adverse Events**

An adverse event (AE) is defined as any untoward medical occurrence associated with the use of an intervention, whether or not considered intervention-related. An AE can therefore be any unfavorable and unintended sign (including an abnormal laboratory finding), symptom, or disease temporally associated with the use of an investigational product [21 CFR 312.32(a), ICH E6(R2)].

All treatment-emergent AEs (TEAEs; AEs occurring at or after randomization) will be coded by preferred term and system organ class (SOC) from the Medical Dictionary for Regulatory Activities (MedDRA), version 22.0 or above, and will be reviewed by the medical monitor or designee. All TEAEs will be summarized as categorical variables (frequency and percent) by treatment group unless otherwise indicated. TEAEs will not be compared between treatment groups.

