6.1.2 Dosing and Administration

Eligible patients will be enrolled into the study and receive lucinactant treatment. Treatment initiation is to begin within 6 hours of enrollment. The time of enrollment is defined as the time at which it has been confirmed that the subject has met all inclusion criteria and has not met any exclusion criteria, and a request to the pharmacy to prepare study drug has been made. Enrollment should occur within 7 days of endotracheal intubation and MV.

Initial Dose

Reconstituted lyophilized lucinactant is administered using the following instillation procedure:

- a. The ventilator will be set at an FiO₂ of 1.00.
- b. To prevent cough and throat closure, the patient may receive a short-acting paralytic.
- c. Lucinactant will be administered via a number 10 French end-hole suction catheter positioned in the trachea at the end of the endotracheal tube. The suction catheter will be inserted into the ventilator's inspiratory tubing via a side-port connector.
- d. The total dose of lucinactant will be divided into four quarter-doses (40 ml). Each quarter-dose will be further sub-divided into aliquots of 20 ml. Each quarter-dose will be instilled in one of the four positions listed below, one aliquot at a time. After each quarter dose, ensure the patient is stable before continuing the dosing.

- 1. Quarter-dose administered with the patient supine and positioned 45° to the right. Each aliquot will be followed by 1 minute of ventilation.
- 2. Quarter-dose administered with the patient supine and positioned 45° to the left. Each aliquot will be followed by 1 minute of ventilation.
- 3. Quarter-dose administered with the patient supine and positioned 45° to the right. Each aliquot will be followed by 1 minute of ventilation.
- 4. Quarter-dose administered with the patient supine and positioned 45° to the left. Each aliquot will be followed by 1 minute of ventilation.

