6.3 Measures to Minimize Bias: Randomization and Blinding

For this study, the study drug (lyophilized lucinactant) is being delivered in an open-label manner and no randomization will occur; thus, no procedures to minimize bias relative to randomization or blinding will be employed.

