8.4.4 Time Period and Frequency for Event Assessment and Follow-Up

The occurrence of an AE or SAE may come to the attention of study personnel during the study, or upon review by a study monitor.

All AEs including local and systemic reactions not meeting the criteria for SAEs will be captured on the appropriate eCRF. All AEs occurring while on study must be documented appropriately regardless of relationship. All AEs will be followed to adequate resolution.

Any medical condition that is present at the time that the participant is screened will be considered as baseline and not reported as an AE. However, if the study participant's condition deteriorates at any time during the study, it will be recorded as an AE.

Changes in the severity of an AE will be documented to allow an assessment of the duration of the event at each level of severity to be performed. AEs characterized as intermittent require documentation of onset and duration of each episode.

The site will record all reportable events with start dates occurring any time after informed consent is obtained until 7 days after the last day of study participation or Day 30 (whichever occurs first). Events will be followed for outcome information until resolution or stabilization, or for 30 days after study participation. When possible, information collection should continue for subjects that withdraw or discontinue treatment early.

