8.4.5 Adverse Event Reporting

All AEs are to be assessed in all subjects throughout Day 30 (from enrollment to study withdrawal or completion) and documented in the study eCRF. Each AE should be reported spontaneously or in response to general, non-directed discussion with the attending nurse or physician (eg, "has there been any change in subject status since the last assessment period?"). For each AE, the investigator should obtain all information required to complete the AE page of the eCRF, in accordance with eCRF completion guidelines (provided separately by Windtree).

All AEs, regardless of seriousness, severity, or relationship to study participation, must be recorded (using medical terminology) in the source document and on the AE page of the eCRF. Whenever possible, diagnoses should be given when signs and symptoms are due to a common etiology.

All AEs must be followed until resolution or until a stable clinical end-point is reached, or for at least 30 days after the subject's last day in the study if an AE is ongoing at the time the subject completes the study.

Documentation of AEs in the eCRF must include the following parameters; (1) duration (time of onset and resolution), (2) severity or grade, (3) outcome, (4) action taken, and (5) relationship to study drug. AEs will be coded using the Medical Dictionary for Regulatory Activities (MedDRA).

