### **5.3.2 AEs Related to Surfactant Administration (AEs of Special Interest)**

Individual air leaks (eg, pneumothorax, pulmonary interstitial emphysema, pneumo-mediastinum, pneumopericardium, and subcutaneous emphysema) will be identified by medical review of all AEs and summarized by treatment group.

Occurrences of apnea, bradycardia, and desaturation after the peri-dosing period will be summarized by treatment group.

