### **5.3.3 Other TEAEs**

TEAEs, other than those listed above, will be summarized by treatment group by the MedDRA preferred term and SOC for all TEAEs, regardless of relationship to study drug, and for TEAEs at least remotely related. If a TEAE occurs multiple times for the same subject within the same term or body system, only the most severe occurrence for that term or body system will be counted.

In addition, all TEAEs will be summarized by severity (mild, moderate, severe), relationship to the study drug (unrelated, unlikely related, possibly related, related), whether or not the TEAE was device related, and, if sufficient number of subjects warrant, by gender, race, and ethnic origin.

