## **7 STATISTICAL TECHNICAL ISSUES**

### **7.1 Methods of Assigning Subjects to Treatment Groups**

Subjects will be enrolled into the lucinactant treatment group if they meet all the screening criteria. Enrolled subjects will receive reconstituted lyophilized lucinactant (30 mg total TPL/mL) as a liquid at 160 ml (~80 mg TPL/kg lean body weight [ $\sim 2.7$  ml/kg lean body weight]). Sites from the US will participate in this study.

This is a single-treatment, open-label study, so there are no randomized procedures.

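### The SAP dates treatment-emergent adverse events from a randomisation that does not take place; read as enrolment, the rule counts events that began before any lucinactant was given

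*SAP*

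**What the plan says.** SAP 5.3 sets the rule for the adverse-event tables: "All treatment-emergent AEs (TEAEs; AEs occurring at or after randomization) will be coded by preferred term".

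Both documents rule out randomisation. Protocol 6.3 says the drug "is being delivered in an open-label manner and no randomization will occur", and SAP 7.1 says "This is a single-treatment, open-label study, so there are no randomized procedures".

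Protocol 6.1.2 places enrolment at the point where eligibility is confirmed and the pharmacy has been asked to prepare drug. It then says "Treatment initiation is to begin within 6 hours of enrollment". SAP 2.2 and 2.2.1 give the same 6-hour limit but count it from randomisation.

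On collection, Protocol 8.4.4 says "The site will record all reportable events with start dates occurring any time after informed consent is obtained", while Protocol 8.4.5 has "All AEs are to be assessed in all subjects throughout Day 30 (from enrollment to study withdrawal or completion".

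On counting, SAP 5.3.3 says that, for repeated events in one subject, "only the most severe occurrence for that term or body system will be counted". SAP 5.3.2 says that air leaks "will be identified by medical review of all AEs and summarized by treatment group". SAP 5.3.4 lists and summarises all SAEs, and where the same SAE recurs in a subject the summary keeps the most severe occurrence. SAP 5.1 restricts the safety population to subjects who received study medication.

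**The concern.** Safety and tolerability is the first-named primary endpoint, and there is no control arm. The adverse-event tables therefore carry the main conclusion, and what counts as treatment-emergent should be fixed by exposure to the drug. As written, the definition has no start point. Under the natural substitute, enrolment, it starts before exposure.

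The patients are ventilated and critically ill, so new events or deterioration while drug is being prepared are plausible. An event with onset in that interval cannot have been caused by lucinactant. It would nevertheless be tabulated as treatment-emergent and, where the most-severe rule applies, might stand in for an event that came after dosing.

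**Working it through.** **Step 1: which start point is meant.** The SAP's 6-hour limit runs from randomisation where the protocol's runs from enrolment. The two words mark the same moment in parallel sentences, so enrolment is the natural reading. On that reading the pre-dose stretch treated as treatment-emergent is at most 6 hours, or 6/720 = 0.8% of a 30-day (720-hour) follow-up.

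**Step 2: are events in that stretch collected?** Yes, on either protocol start point. Consent and enrolment both precede dosing. Conditions present at screening are baseline (Protocol 8.4.4), and abnormalities noted before enrolment go to medical history (Protocol 8.1.3). A new event or a deterioration between enrolment and dosing is still an AE.

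**Step 3: does any population or table rule remove them?**

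| Output | Rule in the SAP | Can a pre-dose event enter? |
|---|---|---|
| Tables 5.3.1–5.3.5, Listing 2.3 (TEAEs) | onset from randomisation, read as enrolment | Yes |
| Table 5.2 (air leaks) | medical review of all AEs | Yes; no onset rule |
| Tables 5.4.1–5.4.4 (SAE summaries) | all SAEs | Yes; no onset rule |
| Tables 5.1.1, 5.1.2 (peri-dosing) | tied to dosing | No |
| Later apnea, bradycardia and desaturation (SAP 5.3.2) | after the peri-dosing period | No |

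The safety population excludes subjects who were never dosed. It does not limit when an event in a dosed subject began.

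**Step 4: size of the main effect.** The plan gives no TEAE rate to reproduce. Its only related figures are the study sizes, and each agrees with its own screening number: SAP 60/20 = 3 screened per subject enrolled; protocol 90/30 = 3. I use the protocol's 30 and show the SAP's 20 alongside.

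- Effect of one subject whose only event of a term is pre-dose: 1/30 = 3.3 percentage points (1/20 = 5.0). If the same subject also has that term after dosing, incidence does not change, because the subject counts once either way.
- Number of such subjects: not derivable from the documents. Purely as an assumption, let a share p of subjects have an event in the window. The expected number is 30p, and the chance of at least one is 1 − (1 − p)^30.

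| Assumed p | Expected of 30 | Chance of at least one, n = 30 | Same, n = 20 |
|---|---|---|---|
| 1% | 0.3 | 26% | 18% |
| 5% | 1.5 | 79% | 64% |
| 10% | 3.0 | 96% | 88% |

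**Step 5: the secondary effect.** Suppose a subject has a severe pre-dose event and a moderate, possibly related post-dose event in the same body system. Under the rule in SAP 5.3.3 the body-system row keeps only the severe, pre-dose one, so its severity and relationship are what the table shows. This needs both events in one subject, the first within at most 6 hours. It also needs the rule to apply: it sits in a paragraph limited to TEAEs not covered in the preceding subsections. The next paragraph summarises all TEAEs by severity and relationship without restating a counting rule, so the scope is arguable. For SAEs the rule is narrower (recurrence of the same SAE), and the listing keeps every occurrence.

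**Step 6: the other uses of the word.** Besides SAP 5.3, the term needs correcting 12 times: Executive Summary 1, 1.2.1 1, 2.2 1, 2.2.1 1, 3.1 2, 4.1 3, 4.1.2 1, 8.2 2. Read as enrolment, the mITT in 1.2.1 and 3.1 becomes the mITT of SAP 4.1.1 and Protocol 9.3, and Days 3 and 30 in SAP 8.2 agree with Day 1 as the day of enrolment. No analysis set changes.

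**The case against.** The strongest reply has four parts.

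*The direction is conservative.* Counting from enrolment adds events and overstates harm. This stands for the main effect. It makes the problem less serious but does not make the label correct.

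*Safeguards exist.* Screening conditions are baseline, 6 hours is a ceiling, and Protocol 8.4.3.2 grades relationship partly on timing, so a pre-dose event should be graded unrelated. The by-relationship tables would then largely separate such events. This stands for those tables, but not for Tables 5.3.1, 5.3.2 and 5.3.5, which do not split by relationship.

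*The air-leak and SAE tables are not wholly unanchored.* The AE definition in SAP 5.3 refers to use of the product, and the heading of SAP 5.3.2 refers to surfactant administration. This stands in part: the link is there but loose. A programmer cannot derive an onset cut-off from it, especially when collection starts at consent or enrolment.

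*The hiding of drug events is remote.* This also stands, given the limited scope of the SAP 5.3.3 rule and the full SAE listing. A reader might infer that the plan systematically masks drug-related harm. The documents do not support that.

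**Conclusion.** The TEAE definition is wrong as written and should be corrected. Read as enrolment, it admits up to 6 hours of pre-lucinactant events to Tables 5.3.1–5.3.5 and Listing 2.3. The main consequence is an overstatement of 3.3 percentage points for each subject whose only event of a term is pre-dose (n = 30). The number of subjects is probably small and cannot be estimated from the documents. Displacement of a post-dose event is possible but rarer. The air-leak and SAE summaries need the same onset rule because they have no operational one.

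A reader might go further and infer that the stray randomisation wording, or the SAP's 20 subjects against the protocol's 30, undermines the efficacy result. It does not. The mITT set and the oxygenation index estimate are unchanged once the word is read as enrolment. The study tests no hypothesis and has no formal sample size calculation, so no power figure is involved. The SAP's title pages are not available for review, so the protocol version it was written against cannot be seen. Those mismatches are housekeeping.

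The conclusion assumes that enrolment is the intended meaning. If it is not, the definition has no start point at all, and the remedy is the same.

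**What to change.** Before database lock:

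1. In SAP 5.3, define a TEAE as an AE with onset or worsening at or after the start of the first lucinactant administration.
2. Apply the same onset rule to the summaries in Tables 5.2 and 5.4.1–5.4.4.
3. Keep every SAE in Listing 2.2, with pre-dose ones flagged.
4. Add one listing of events between enrolment and first dose, including air leaks and SAEs.

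The cost is a text revision, one short listing and possibly slightly lower counts. No new data or protocol change is needed: Protocol 8.4.5 already requires the time of onset, and Protocol 8.4.4 already requires changes in severity to be documented.

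Housekeeping in the same revision, with no effect on results:

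- Replace the other 12 uses of the randomisation wording with enrolment, or delete them where they refer to an assigned arm or qualify the safety population.
- Use the SAP 4.1.1 mITT definition throughout.
- Reconcile the 24-hour Day 1 in the Executive Summary with the calendar Day 1 in SAP 8.2.
- Align with protocol version 2.1: subjects (20 against up to 30), screened (60 against 90), sites (about 10 in the US against about 15 in the US and Argentina), enrolment period (3–4 against 7–8 months) and last visit (4–5 against 8–9 months).

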## 2.2 Study Design and Randomization

This is a multicenter, single-treatment study in adults with COVID-19, who are being cared for in a critical care environment. Preliminary data from animal and adult human studies indicate that lucinactant could benefit those with ARDS in the context of COVID-19 infection, improving oxygenation and lessening lung damage. Furthermore, lucinactant, given early in the course of the disease, could potentially decrease the need for endotracheal intubation and mechanical ventilation.

Subjects will be enrolled into the lucinactant treatment group if they meet all the screening criteria. Treatment initiation is to begin within 6 hours of randomization. Enrolled subjects will receive reconstituted lyophilized lucinactant (30 mg total TPL/mL) as a liquid at 160 ml (~80 mg TPL/kg lean body weight [~2.7 ml/kg lean body weight]). Sites from the US will participate in this study.

For this study, the study drug (lyophilized lucinactant) is being delivered in an open-label manner. No procedures to minimize bias relative to randomization or blinding will be employed.

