### **8.1 Baseline Definition**

Baseline is defined as the measurements at the start of study drug administration for subjects enrolled in the treatment.

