### **8.2 Windows for Visits**

Accurate clock times will be recorded for each timed event in military time (24-hour clock). Day 1 is the day of enrollment; Day 2 begins at midnight following enrollment; Day 3 is the 2nd day following randomization; Day 30 will be the 29th day after the day of randomization.

All assessments at pre-specified time points are to be conducted within the windows specified in the protocol. Summary tables will use the pre-specified time points, not the actual times, to summarize the data.

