- 4.9.1 Efficacy Analysis – Plateau Pressure and Peak Inspiratory Pressure (PIP) through 24 Hours – Modified Intent-to-Treat Population
- 4.9.2 Efficacy Analysis – Plateau Pressure and Peak Inspiratory Pressure (PIP) through 24 Hours – Intent-to-Treat Population
- 4.10.1 Efficacy Analysis – Ventilation Index (VI) through 24 Hours – Modified Intent-to-Treat Population
- 4.10.2 Efficacy Analysis – Ventilation Index (VI) through 24 Hours – Intent-to-Treat Population
- 4.11.1 Efficacy Analysis – Lung Compliance (Dynamic) through 24 Hours – Modified Intent-to-Treat Population
- 4.11.2 Efficacy Analysis – Lung Compliance (Dynamic) through 24 Hours – Intent-to-Treat Population
- 4.12.1 Efficacy Analysis – Daily Lung Compliance (Static) on Ventilator – Modified Intent-to-Treat Population
- 4.12.2 Efficacy Analysis – Daily Lung Compliance (Static) on Ventilator – Intent-to-Treat Population
- 4.13.1 Efficacy Analysis – Ventilator Free Days – Modified Intent-to-Treat Population
- 4.13.2 Efficacy Analysis – Ventilator Free Days – Intent-to-Treat Population
- 4.14.1 Efficacy Analysis – Days in the Intensive Care Unit (ICU) – Modified Intent-to-Treat Population
- 4.14.2 Efficacy Analysis – Days in the Intensive Care Unit (ICU) – Intent-to-Treat Population
- 4.15.1 Efficacy Analysis – Days in the Hospital – Modified Intent-to-Treat Population
- 4.15.2 Efficacy Analysis – Days in the Hospital – Intent-to-Treat Population
- 4.16.1 Efficacy Analysis – Incidence of All-Cause Mortality – Modified Intent-to-Treat Population
- 4.16.2 Efficacy Analysis – Incidence of All-Cause Mortality – Intent-to-Treat Population
- 4.17.1 Efficacy Analysis – Organ Failure Free Days – Modified Intent-to-Treat Population
- 4.17.2 Efficacy Analysis – Organ Failure Free Days – Intent-to-Treat Population
- 5.1.1 Peri-Dosing Adverse Events – Initial Dose – Safety Population
- 5.1.2 Peri-Dosing Adverse Events – Repeat Doses – Safety Population
- 5.2 Air Leaks – Safety Population
- 5.3.1 Treatment-Emergent Adverse Events by System Organ Class and Preferred Term – Safety Population
- 5.3.2 Treatment-Emergent Adverse Events by System Organ Class and Preferred Term by Severity – Safety Population
- 5.3.3 Treatment-Emergent Adverse Events by System Organ Class and Preferred Term by Relationship to Study Treatment – Safety Population
- 5.3.4 Treatment-Emergent Adverse Events by System Organ Class and Preferred Term by Severity and Relationship to Study Treatment – Safety Population

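### SAP 5.3 starts treatment-emergent AEs at a randomization that never occurs, so an AE or air leak that begins after screening but before the first dose would be counted with post-dose events

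*SAP*

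**What the plan says.** SAP 5.3 defines the class used for the adverse event tables: "All treatment-emergent AEs (TEAEs; AEs occurring at or after randomization". SAP 7.1 states "This is a single-treatment, open-label study, so there are no randomized procedures", and Protocol 6.3 agrees.

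Elsewhere the SAP uses the same word for enrollment. SAP 2.2 has "Treatment initiation is to begin within 6 hours of randomization", where Protocol 6.1.2 has "Treatment initiation is to begin within 6 hours of enrollment". SAP 8.2 begins with "Day 1 is the day of enrollment; Day 2 begins at midnight following enrollment" and then counts Day 3 and Day 30 from randomization. For efficacy the time origin is different: "Baseline is defined as the measurements at the start of study drug administration" (SAP 8.1).

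For air leaks, SAP 5.3.2 says that individual events "will be identified by medical review of all AEs and summarized by treatment group". The planned output is Table 5.2, titled "Air Leaks – Safety Population". SAP 5.1 defines that population as anyone who received study drug.

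**The concern.** Safety and tolerability form a primary endpoint (SAP 1.2.2), and air leak is the AE of special interest (Protocol 8.4.8). Protocol 2.4.1 names air leak as a complication of mechanical ventilation itself, and every subject is ventilated at entry. With one arm there is no background rate for comparison. Whether a leak began before or after the first instillation is then the simplest available separation of ventilator events from possible drug events.

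The SAP does not make that separation. Its TEAE cut is tied to an event that does not happen, and the nearest real event comes before dosing. For air leaks no onset condition is given at all. The same TEAE definition governs Tables 5.3.1 to 5.3.5 and Listing 2.3, so the effect is not confined to air leaks.

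**Working it through.** The plan states no air-leak rate and no sample size formula, so there is no figure of its own to reproduce. The check has two parts: tracing the definitions, then sizing one misplaced event.

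**1. Where the TEAE cut falls.** Read literally, it has no date. Read as enrollment, which is how SAP 2.2 and 8.2 use the word, it falls up to 6 h before the first dose (Protocol 6.1.2).

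**2. Which air leaks are eligible.** SAP 5.3.2 draws on all AEs. Recording starts at consent under Protocol 8.4.4 and at enrollment under 8.4.5. SAP 5.3.3 then turns to the remaining TEAEs, which suggests that air leaks are meant to be TEAEs, but that cut still precedes dosing. The safety population limits who is counted, not when an event began.

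**3. What the protocol removes.** A condition present at screening is baseline and becomes an AE only if it deteriorates (Protocol 8.4.4). Clinically significant abnormalities noted before enrollment go to medical history (Protocol 8.1.3). Screening takes place at most 24 h before dosing (Protocol 10.1.1.2). So the exposed events are those starting:
- between enrollment and first dose, at most 6 h; or
- on the widest reading, between screening and first dose, up to about 24 h. This needs a finding made before enrollment to be recorded as an AE despite 8.1.3.

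**4. Size of one misplaced leak.** The documents differ on N: up to 30 (Protocol 9.2) or 20 (SAP 2.2.3). One event adds 1/30 = 3.3 points or 1/20 = 5.0 points. The exact (Clopper-Pearson) 95% limits for x events in n are the 0.025 quantile of Beta(x, n−x+1) and the 0.975 quantile of Beta(x+1, n−x); at x = 0 the lower limit is 0.

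| Leaks counted | N=30 | N=20 |
|---|---|---|
| 0 | 0% (0 to 11.6) | 0% (0 to 16.8) |
| 1 | 3.3% (0.1 to 17.2) | 5.0% (0.1 to 24.9) |
| 2 | 6.7% (0.8 to 22.1) | 10.0% (1.2 to 31.7) |

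One pre-dose leak moves the result down one row.

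**5. How likely is even one? (assumption only)** The documents give no leak rate. Assume a 30-day (720 h) leak risk R of 5% to 20% and a constant hazard. For a window of w hours, P(at least one) = 1 − (1−R)^(w·n/720).
- w = 6, n = 20: the exponent is 120/720 = 1/6, giving 0.9% to 3.7%.
- w = 6, n = 30: the exponent is 180/720 = 1/4, giving 1.3% to 5.4%.
- w = 24, n = 20: the exponent is 480/720 = 2/3, giving 3.4% to 13.8%.
- w = 24, n = 30: the exponent is 1, giving 5.0% to 20.0%.

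If the hazard in the pre-dose window were five times the average, the 6 h figures become 4.2% to 17.0% (n=20) and 6.2% to 24.3% (n=30). The 24 h figures become 15.7% to 52.5% and 22.6% to 67.2%. That last case combines the widest window with an assumed high hazard, and nothing in the documents supports or excludes it.

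**The case against.** The strongest reply is that little can go wrong in practice. Leaks present at screening are already excluded, the window is hours long, and the most likely effect on Table 5.2 is none. The 3.3 and 5.0 points are simply 1/N and would apply to any single misclassified event. An error in this direction raises the safety count, so it is conservative. Several safeguards exist: air leaks are reported within 24 h of awareness (Protocol 8.4.8), the investigator grades relationship partly on timing (8.4.3.2), TEAEs are tabulated by relationship (Table 5.3.3) and listed (Listing 2.3), and the DMC meets after every 6 subjects (10.1.6.2). The SAP's general AE definition also speaks of events associated with use of the product, and the heading of SAP 5.3.2 points to surfactant administration.

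Most of this stands, and it is why the point is minor. It does not rescue the definition. The general wording and the heading are not an onset rule, and none of the safeguards is specified as changing the Table 5.2 count. An overcount is still a wrong rate where no control arm can absorb it.

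Three stronger readings are tempting and are not supported:
- **Every leak that began before drug is counted.** It is not, because of the screening and medical-history rules above.
- **Table 5.2 has no split by onset.** The SAP gives only a title and no table shell. The most that can be said is that no split is specified.
- **The first dose needs a pneumothorax check because retreatment has one.** That is a separate eligibility question, partly covered by the entry radiograph, the screening examination and the investigator's judgment on starting treatment. It does not follow from the TEAE definition.

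**Conclusion.** The TEAE definition is wrong as written, and the severity is minor. It names an event that does not occur; read as enrollment, it labels AEs up to 6 h before any drug as treatment-emergent. Air leaks have no stated onset condition. The affected events are those that start after screening and before the first dose in a subject who is then dosed. Each such leak adds 3.3 points (N=30) or 5.0 points (N=20) to the air-leak rate.

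This rests on two assumptions: that randomization means enrollment in SAP 5.3, and that no unseen table shell supplies an onset split. The chance that such a leak occurs is not in the documents. It is probably low over the 6 h window, but that is a judgment resting on assumed rates. A reader should not conclude that the reported air-leak rate will be wrong, only that the rule allows it to be.

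**What to change.** In SAP 5.3, define a TEAE as an AE that starts, or worsens, at or after the start of the first dose. This matches the baseline in SAP 8.1 and keeps a pre-existing leak that deteriorates after dosing in the count. In SAP 5.3.2 and Table 5.2, count treatment-emergent air leaks on that definition, and list separately any leak recorded as an AE with onset before the first dose.

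The cost is a small SAP edit and one extra listing line. No new data are needed, because Protocol 8.4.5 already requires the onset time of each AE, and no protocol change is involved.
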